8.0 TRIAL PROCEDURES

8.1 Trial Procedures

The Trial Flow Chart - Section 7.0 summarizes the trial procedures to be performed at each visit. Individual trial procedures are described in detail below. It may be necessary to perform these procedures at unscheduled time points if deemed clinically necessary by the investigator.

8.1.1 Tumor Tissue Collection and Correlative Studies Blood Sampling

Biomarker analyses will be used to investigate the effect of the spartalizumab and siltuximab at the molecular and cellular level as well as to determine how changes in the markers may relate to exposure and clinical outcomes. In addition, potential predictive markers of efficacy, as well as mechanisms of resistance to spartalizumab and siltuximab treatment will also be explored.

While the goal of the biomarker assessments is to provide supportive data for the clinical study, there may be circumstances when a decision is made to stop a collection, or not perform or discontinue an analysis due to either practical or strategic reasons (e.g., inadequate sample number, issues related to the quality of the sample or issues related to the assay that preclude analysis, impossibility to perform correlative analyses, etc.). Therefore, depending on the results obtained during the study, sample collection analysis may be omitted at the discretion of the PI.

The sample collection information must be entered on the appropriate sample collection log eCRF page(s) and requisition form(s). Detailed instructions for the collection, handling, and shipment of tumor samples are outlined in the laboratory manual for the study.

Samples collected for research purposes include blood and tissue. Blood is not optional. The samples will be used to evaluate correlative markers for this study and will be stored and may be used for other research in the future. Tissue biopsies performed as part of the trial will only be done in a subset of patients and are optional. Tissue biopsies will only be performed during the expansion phase. Tissue will used to evaluate correlative markers for this study and will be stored and may be used for other research in the future.

All correlative samples will be de-identified. A study specific subject number will used to identify the samples. The study specific subject number will be linked to the patient information only in our HIPPA compliant electronic CRF.

Samples will be handled and stored in [name] lab (Winship Bldg. C 3rd floor).

During the study, both blood and tumor samples will be collected to perform exploratory biomarker assessments. These are summarized in Table 10

Protocol/Version No.: 5, Date December 15, 2022

Table 10 Biomarker sample collection plan

rate of the state			
Sample type	Volume	Visit	Time point
Optional: Paired biopsies pre and post treatment for patients on the expansion phase Core, excisional and incisional biopsies are acceptable.		Pretreatment And days 14-21 of cycle 1	pretreatment days 14 to 21 of cycle 1
Blood samples as detailed in study calendar		I	

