6.3.5 Trial Blinding/Masking

This is an open-label trial; therefore, the Sponsor, investigator and subject will know the treatment administered.

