8.1.1.1 Biomarker assessments in tumor samples

Pre- and post- treatment tumor biopsies will be obtained from 24 patients enrolled on the expansion phase. Patients will sign the optional biopsy consent prior to starting treatment and will be assigned to either start spartalizumab or spartalizumab / siltuximab for the first cycle. Biopsies will be obtained within 4 weeks prior to the first dose of study therapy (biopsy #1) and then during the third week between Day 14 and Day 20. At least three core biopsies will be obtained at the time of the biopsy (unless limited for technical/safety reasons). The obtained tissues will be handled in the following way:

- 1) RNAlater for RNA stabilization and tissue storage
- 2) Formalin-fixed paraffin block with one cut H&E stained slide
- 3) Liquid nitrogen frozen tissue in cryo-preservation vials

All collected tissues are stabilized and stored in -80°C freezers (RNAlater stabilized, OCT embedded, short term storage) or the vapor phase of a liquid nitrogen freezer (long term storage) in single use aliquots. All FFPE tissue blocks are stored in a climate controlled storage room that is temperature (less than 27°C) and humidity controlled.

Tissue will be evaluated using IHC for CD3, CD4, CD8, CD163, PD-1, PD-2, PDL-1, MIF, TAM and stromal/vascular markers. Tissue will also be dissociated and flow cytometry will be used to determine the characteristics of macrophages and lymphocytes. Genomic (transcriptome) profiling will be performed on tissue and lymphocytes.

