12.2 Statistical and Analytical Plans

Summary statistics will be presented for all safety, efficacy and biomarker parameter analyses. The purpose of these analyses is hypothesis generating and therefore, formal statistical testing will not be performed. Various exploratory statistical tests may be applied to data generated from this trial to generate hypotheses to be tested in subsequent trials. In general, data for continuous parameters will be presented using descriptive statistics including sample size, mean, and median; standard deviation; and minimum and maximum. Categorical parameters (such as pathologic response rate) will be displayed using counts and percentages. Toxicities will be presented as worst toxicity per patient and will be reported as percent toxicity.

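### Section 8.1.1 lets biomarker analyses be omitted for undefined strategic reasons and according to results, with no duty to report omissions, which could exaggerate the exploratory marker changes that remain

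*Combined protocol and SAP*

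**What the plan says.** Section 8.1.1 allows the study to stop a collection, or to "not perform or discontinue an analysis due to either practical or strategic reasons". Its examples are "inadequate sample number, issues related to the quality of the sample or issues related to the assay that preclude analysis", followed by correlative analyses proving impossible. The list is left open, and strategic is not defined. The paragraph then concludes: "Therefore, depending on the results obtained during the study, sample collection analysis may be omitted at the discretion of the PI".

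Section 8.1.1.1 sets out what is planned in tissue: "Tissue will be evaluated using IHC for CD3, CD4, CD8, CD163, PD-1, PD-2, PDL-1, MIF, TAM and stromal/vascular markers". Flow cytometry and transcriptome profiling are added. On numbers it says: "Pre- and post- treatment tumor biopsies will be obtained from 24 patients enrolled on the expansion phase". Section 8.1.1 describes the same biopsies as optional and done in a subset. Section 8.1.1.2 adds blood markers in all patients.

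On reporting, section 12.2 says: "Summary statistics will be presented for all safety, efficacy and biomarker parameter analyses". It calls the analyses hypothesis generating, rules out formal testing, and then allows exploratory work: "Various exploratory statistical tests may be applied to data generated from this trial to generate hypotheses to be tested in subsequent trials".

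On who can see what, section 6.3.5 says: "This is an open-label trial; therefore, the Sponsor, investigator and subject will know the treatment administered". Section 12.1 has the PI assign the cycle 1 regimen in the expansion phase.

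**The concern.** This is a written permission, not a gap in detail. The person who may omit an analysis works in an open-label trial, and the stated trigger is the results. Section 5.4.1.2 also records that a difference between the cycle 1 regimens is anticipated, so there is a hoped-for finding.

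The markers are the only evidence on the exploratory objective in section 3.3, which the synopsis lists as a secondary objective. Section 12.1 says the paired samples can help develop the combination further. With no formal test and no multiplicity rule, a reader can judge a marker signal only by knowing how many markers were examined and how many were set aside. If unpromising markers were dropped part-way, those left would tend to look better than they are, and the report would not have to say so.

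**Working it through.** The documents give no sample size, effect size or error rate for the biomarkers, so there is no figure of the plan's own to reproduce. The check has two parts.

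**1. Does any other text close the gap?**

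- The commitment in section 12.2 covers analyses. An assay never run, or discontinued under 8.1.1, is not clearly among them.
- The sample collection log required by 8.1.1 records collection. It does not record which assays were dropped or why.
- The marker list in 8.1.1.1 states intent. Section 8.1.1 permits departures from it, and nothing requires planned to be set against completed.
- No section says that the decision must be made without sight of marker or clinical results.

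**2. How large could the effect be?**

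Assumptions, none of them in the protocol: changes are measured in SDs of the paired difference. A marker is looked at after half the pairs and continued only if its interim z exceeds a threshold c. The 24 pairs come from 8.1.1.1. Twelve is used because biopsies are optional and patients are divided between two cycle 1 regimens in a ratio that is not stated.

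With n1 pairs at the look and as many after it, the second half carries no selection. For a marker with no true change:

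expected final change = 0.5 × E[z1 | z1 > c] / √n1, where E[z1 | z1 > c] = φ(c) / (1 − Φ(c)).

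- c = 0 (continue if the sign is favourable): 0.399/0.500 = 0.798
- c = 1: 0.242/0.159 = 1.525

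| Pairs (look) | c | Calculation | Exaggeration, true change 0 |
|---|---|---|---|
| 24 (12) | 0 | 0.5 × 0.798/√12 | 0.115 SD |
| 24 (12) | 1 | 0.5 × 1.525/√12 | 0.22 SD |
| 12 (6) | 0 | 0.5 × 0.798/√6 | 0.16 SD |
| 12 (6) | 1 | 0.5 × 1.525/√6 | 0.31 SD |

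Simulation of 400,000 null markers gave the same values for the three cases it covered (0.115, 0.221 and 0.310 SD).

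A second calculation used no interim look. It simulated nine null markers (the number named for IHC) 20,000 times, with correlation 0 or 0.5, and selected on the final results:

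| Rule | 24 pairs | 12 pairs |
|---|---|---|
| All reported, or dropped for reasons unrelated to results | 0.00 | 0.00 |
| Favourable changes only | 0.16 | 0.23 |
| Best 5 of 9 | 0.09 to 0.13 | 0.13 to 0.19 |
| Best 3 of 9 | 0.14 to 0.20 | 0.20 to 0.29 |
| Best only | 0.21 to 0.30 | 0.30 to 0.43 |

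**With a true change of 0.3 SD**, c in the formula becomes c − 0.3√n1. For 24 pairs, 0.3√12 = 1.039:

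- c = 0: φ(−1.039)/(1 − Φ(−1.039)) = 0.2325/0.8507 = 0.273, so 0.5 × 0.273/√12 = 0.04 SD (against 0.115)
- c = 1: φ(−0.039)/(1 − Φ(−0.039)) = 0.3986/0.5156 = 0.773, so 0.5 × 0.773/√12 = 0.11 SD (against 0.22)

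Keeping only favourable final changes adds about 0.03 SD (0.33 − 0.30). Ranking rules are the exception: if all nine markers share the same true change the ranking is unaltered, and the best 5 of 9 still gain 0.13 SD (0.432 − 0.300, uncorrelated markers).

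**The case against.** The strongest reply is that the sentence opens with a word of consequence and follows examples that all concern feasibility. On that reading the results that matter are too few samples, poor samples or a failed assay, and omission on those grounds gives 0.00 SD. The reply adds that the tissue markers are named in advance, that 12.2 commits to summarising the biomarker analyses with sample sizes, and that anyone holding the protocol can see which named markers are missing from a report. The analyses are hypothesis generating and feed no decision on dose, stopping or response.

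Much of this stands. A reader might infer that the reported marker effects are biased upward. The documents do not support that: they give a permission, not a practice, and no common direction is stated for the nine markers, so the risk is exaggeration in whichever direction is favoured. A reader might also attach a false-positive rate. Under the c = 1 rule with 24 pairs, 12.6% of continued null markers exceed z = 1.96, against 2.5% unselected. That rate belongs to a formal test which 12.2 says will not be performed.

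What does not stand is the claim that the text is already safe. Strategic is offered as an alternative to practical, the list of examples is open, and the conclusion names results rather than samples or assays. A missing marker can be noticed only if it is among those named, and the reason for its absence need not be given.

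**Conclusion.** The concern holds as a risk that the wording permits. Result-driven omission would comply with section 8.1.1 and need not be disclosed. Under the continuation rules tried, a marker with no true change would be overstated by about 0.1 to 0.3 SD. Selecting on final results gives 0.09 to 0.43 SD, the top of that range being the single best of nine uncorrelated markers with 12 pairs. Where markers truly change, sign and threshold rules exaggerate less. All these sizes rest on assumed rules, since the protocol schedules no marker look and sets no threshold. They are not evidence that bias has occurred or will occur. The recommended phase II dose and the response-rate conclusion do not depend on the markers and are unaffected. The change is worth making because it is cheap and because exploratory results are hard to interpret without a complete list of what was examined.

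**What to change.** In section 8.1.1, delete the strategic ground and the clause that makes omission depend on study results. Replace them with text to this effect:

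- Collection or analysis of a planned marker may be omitted only for sample quantity or quality, assay failure, biopsy safety or technical limits, a declined optional biopsy, or withdrawal of consent. If tissue or budget is limited, cuts follow a marker and assay priority order fixed in advance.
- The decision is made without reference to marker or clinical results, and its date and reason are logged.
- The report lists each marker named in 8.1.1.1 and 8.1.1.2, and each assay platform (flow cytometry, transcriptome), with the number of patients or pairs collected, analysed and omitted, and why.

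This keeps every feasibility ground that the section now names and does not oblige the study to assay every stored sample. It needs a few sentences, a priority list and one table, with no extra patients or procedures. The downside is small: the PI can no longer save assay cost or tissue by dropping markers that look uninteresting.

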8.1.1.1 Biomarker assessments in tumor samples

Pre- and post- treatment tumor biopsies will be obtained from 24 patients enrolled on the expansion phase. Patients will sign the optional biopsy consent prior to starting treatment and will be assigned to either start spartalizumab or spartalizumab / siltuximab for the first cycle. Biopsies will be obtained within 4 weeks prior to the first dose of study therapy (biopsy #1) and then during the third week between Day 14 and Day 20. At least three core biopsies will be obtained at the time of the biopsy (unless limited for technical/safety reasons). The obtained tissues will be handled in the following way:

- 1) RNAlater for RNA stabilization and tissue storage
- 2) Formalin-fixed paraffin block with one cut H&E stained slide
- 3) Liquid nitrogen frozen tissue in cryo-preservation vials

All collected tissues are stabilized and stored in -80°C freezers (RNAlater stabilized, OCT embedded, short term storage) or the vapor phase of a liquid nitrogen freezer (long term storage) in single use aliquots. All FFPE tissue blocks are stored in a climate controlled storage room that is temperature (less than 27°C) and humidity controlled.

Tissue will be evaluated using IHC for CD3, CD4, CD8, CD163, PD-1, PD-2, PDL-1, MIF, TAM and stromal/vascular markers. Tissue will also be dissociated and flow cytometry will be used to determine the characteristics of macrophages and lymphocytes. Genomic (transcriptome) profiling will be performed on tissue and lymphocytes.

8.1.1.2 Biomarker assessments in plasma

All patients participating in the study will be requested to provide a mandatory whole blood samples (approximately 20 mL each), collected at study treatment baseline (Pre-dose) and at specific time points during treatment (Table 7.6). The plasma will be used to measure cytokines levels (and/or other circulating markers) to correlate with antitumor activity of spartalizumab. The changes of cytokines (or other markers) related to immune response will

Protocol/Version No.: 5, Date December 15, 2022

be assessed to explore spartalizumab activity (e.g. assessing interferon gamma response cytokines).

Approximately 20 mL of peripheral blood samples will be collected prior to initiation of study therapy, on day 1 of the first 3 cycles. The peripheral blood mononuclear cells will be isolated from these samples and stored in -80°C freezers until analysis. Samples will be evaluated for:

- i. Determine whether there is an increase in expression of T-cell co-stimulatory markers in PBMCs after treatment. Samples will be collected at baseline and every other week for the first 9 weeks. Analysis will include proportion of T, B, NK, memory and effector T cell subsets and expression of PD-1, PD-L1 and B7 family members.
- ii. Determine whether changes in ex vivo functional assays for PBMCs post treatment correlate with response. Samples will be collected at baseline and on weeks 6 and 9. This will be performed using interferon- gamma and CD107.

8.1.1.3 Biomarker Germline DNA analysis

A mandatory blood sample will be obtained from all patients participating in the study. One whole blood (6mL) sample will be collected at any time during screening. The 6mL sample will be used for germline DNA analysis. The germline DNA will be used to compare with genetic sequences found in tumor DNA of the same patients that differ from reference genes sequences; the goal is to determine if any difference of tumor DNA, from reference gene sequences is of somatic or germline origin. In addition eventual polymorphism of PD1, PD-L1 and PD-L2 may be assessed in germline DNA.

Protocol Study No:

Product: Siltuximab and Spartalizumab

Protocol/Version No.: 5, Date December 15, 2022

8.1.2 Screening

A patient who has a laboratory test result(s) that does not satisfy the entrance criteria may have the test(s) repeated. These test(s) may be repeated as soon as the investigator believes the retest result(s) is/are likely to be within the acceptable range to satisfy the entrance criteria, but should be completed within approximately 3 weeks of the original screening visit date. In this case, the subject will not be required to sign another ICF, and the original patient ID number assigned by the investigator will be used. In the event that the laboratory test(s) cannot be performed within 3 weeks of the original screening visit, or the re-test(s) do not meet the entrance criteria, or other eligibility criteria have changed and are not met anymore, the patient is considered a screen failure, and must be discontinued from the study.

A new ICF will need to be signed if the investigator chooses to re-screen the patient after a patient has screen failed, however, the patient ID number will remain the same. All required screening activities must be performed when the patient is re-screened for participation in the study. An individual patient may only be re-screened once for the study. Once the number of patients screened and enrolled is likely to ensure target enrollment, the Sponsor may close the study to further screening. In this case, the patients who screen failed will not be permitted to re-screen.

All subjects must sign an informed consent document prior to the initiation of any study related procedures. The informed consent document must be signed within 28 days of Cycle 1 Day 1. Screening procedures (with the exception of the scans) are to be conducted within 28 days of Cycle 1 Day 1.

- Review of study eligibility criteria
- Medical History
- Record concomitant medications taken up to 28 days prior to day 1 cycle 1
- Vitals [temperature, heart rate (HR), blood pressure (BP) and respiratory rate (RR)]
- Physical Examination, including height and weight
- ECOG Performance Status evaluation (within 10 days or less of cycle 1 day 1)
- Laboratory Assessments
 - Hematology: hemoglobin, hematocrit, red blood cell count, white blood cell count with differential and platelet count
 - o Serum chemistry: sodium, potassium, chloride, bicarbonate, magnesium, calcium, phosphorus, blood urea nitrogen, creatinine, total bilirubin, LDH, total protein, ALP, ALT, AST, uric acid and albumin. Fasting glucose.
 - o Serum or urine pregnancy test for women of childbearing potential
 - o Prothrombin time (PT) and activated partial thromboplastin time (aPTT)
 - Urinalysis
 - Tumor markers(when applicable such as known elevated tumor markers): CA19-9

Protocol Study No:

Product: Siltuximab and Spartalizumab

Protocol/Version No.: 5, Date December 15, 2022

o T3, FT4, TSH

- HBV-DNA, Hepatitis B surface antigen (HBsAg), Hepatitis B core antibody (HBcAb), Hepatitis B surface antibody (HBsAb), HCV RNA-PCR
- o HIV, if clinically indicated
- 12-lead ECG
- Radiologic imaging studies to evaluate tumor status. contrast computed tomography (CT) or magnetic resonance imaging (MRI) of the chest and abdomen and pelvis. Additional imaging may be obtained as clinically indicated. Baseline scans may be done within 8 weeks prior to cycle 1 day 1.
- Baseline fresh biopsy (in selected group) will be obtained with 28 days of day1 cycle 1 and after consent is signed.

8.1.2.1 Information to be collected on screening failures

Patients who sign an informed consent but fail to be started on treatment for any reason will be considered a screen failure. The reason for not being started on treatment will be entered in the patient's electronic research records. The demographic information, informed consent, and Inclusion/Exclusion pages must also be completed for Screen Failure patients. No other data will be entered into the clinical database for patients who are screen failures, unless the patient experienced a Serious Adverse Event during the Screening Phase (see Section 8 for SAE reporting details).

8.1.2.2 Patient demographics and other baseline characteristics

Baseline demographic data will be collected on all patients include: gender, race, and age. Past medical history, concomitant medications, family history and prior treatments for pancreatic cancer will be collected at baseline.

8.1.3 Treatment period

Day 1 (±3 days) of each cycle

- Record concomitant medications
- Vitals (temperature, HR, BP and RR)
- History and physical exam
- ECOG performance status
- Toxicity assessment
- Laboratory Assessments
 - Hematology hemoglobin, hematocrit, red blood cell count, white blood cell count with differential and platelet count

71

Protocol Study No:

Product: Siltuximab and Spartalizumab

Protocol/Version No.: 5, Date December 15, 2022

 Chemistry sodium, potassium, chloride, bicarbonate, magnesium, calcium, phosphorus, blood urea nitrogen, creatinine, glucose (random), total bilirubin, LDH, total protein, ALP, ALT, AST, and albumin

- o Tumor markers when applicable
- o T3, FT4, TSH cycle 2 and then after every 3 cycle
- o Uric acid every other cycle
- o For the cycle1 day 1 labs, blood samples from the screening tests maybe used if completed within 1 week of day 1
- Blood sample 20 cc for correlative work (only cycle 1, 2, 3)
- Spartalizumab and siltuximab will be administered as IV infusion every 3 weeks. Given the variability of infusion pumps, a window of -5 minutes and +10 minutes is permitted.
- In selected case in patients receiving paired biopsies siltuximab maybe held in cycle 1

Days 8 and 15 (± 1 day) in cycle 1 and 2 ONLY

- Record concomitant medications
- Vitals (temperature, HR, BP and RR)
- History and physical exam
- ECOG performance status
- Toxicity assessment
- Blood sample 20 cc for correlative work (only cycle1)
- Laboratory Assessments
 - Chemistry sodium, potassium, chloride, bicarbonate, magnesium, calcium, phosphorus, blood urea nitrogen, creatinine, glucose (random), total bilirubin, LDH, total protein, ALP, ALT, AST, and albumin

Between days 14-21 cycle 1

• Repeat biopsy in selected cases.

Every Month

Pregnancy test for women of child bearing potential

72

Product: Siltuximab and Spartalizumab

Protocol/Version No.: 5, Date December 15, 2022

Every 3 cycles between day 15 and 21

• Repeat cross sectional imaging (CT or MRI)

End of treatment visit

- Vitals (temperature, HR, BP and RR)
- History and physical exam
- ECOG performance status
- Toxicity assessment
- Laboratory Assessments
 - Hematology hemoglobin, hematocrit, red blood cell count, white blood cell count with differential and platelet count
 - Chemistry sodium, potassium, chloride, bicarbonate, magnesium, calcium, phosphorus, blood urea nitrogen, creatinine, glucose (random), total bilirubin, LDH, total protein, ALP, ALT, AST, and albumin
 - o Tumor markers when applicable
 - o T3, FT4, TSH cycle 2 and then after every 3 cycle
 - o Blood sample 20 cc for correlative work

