6.3.3 Dose modifications Siltuximab

Table 9. Dose reduction steps for siltuximab

Overall, patients with AEs suspected to be related to siltuximab include pruritus, increased weight (edema), rash, hyperuricemia, and upper respiratory tract infection. Rare side effects include gastrointestinal perforation.

Each patient can receive a maximum of 2 dose reductions of siltuximab prior to permanent discontinuation of siltuximab.

Siltuximab can be held for a maximum of 12 weeks, if no resolution of toxicity to grade 1 or less, then siltuximab will be permanently discontinued.

Dose reduction*											
Starting dose level – 0 Dose level – 1 Dose lev											
Siltuximab	11 mg/kg	9 mg/kg	6 mg/kg **								
*Dose reduction should be based on the worst toxicity demonstrated at the last dose.											
**Dose reduction below 6 mg/Kg is not allowed.											

- 1. Weight gain due to edema **grade 1 or 2** manage symptomatically with diuretics. Patients with **grade 3** hold siltuximab treat symptomatically resume at one dose level lower once grade 1. Patients with **grade 4** hold siltuximab and treat symptomatically. Permanently discontinue siltuximab for first occurrence of grade 4 weight gain.
- 2. Hyperuricemia grade 1 or 2 continue treatment with siltuximab and monitor. Grade 3 start therapy for hyperuricemia (allopurinol) and hold siltuximab until it resolves to grade 1. Resume at a lower dose level. Grade 4 hold siltuximab permanently, treat hyperuricemia (rasburicase).

Protocol/Version No.: 5, Date December 15, 2022

3. Upper respiratory tract infection grade 1 and 2 treat infection and continue siltuximab. Grade 3 or 4 hold siltuximab treat infection. First occurrence of grade 4 upper respiratory tract infection will lead to permanent discontinuation of siltuximab. For Grade 3, resume after infection treated no dose reduction for first occurrence. Dose reduce by one dose level for second occurrence. Hold permanently for third occurrence.

- 4. Pruritus grade 1 and 2 treat symptomatically and continue siltuximab. Grade 3 hold siltuximab, treat symptomatically, resume siltuximab after symptoms resolve.
- 5. Gastrointestinal perforation any grade permanently hold siltuximab.
- 6. Dose modifications of siltuximab for hematologic and non-hematologic toxicities also review 6.3.2.2.

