7.0 TRIAL FLOW CHART

7.1 Study Flow Chart

Trial Period:	Treatment Cycles ^a									End of Treatment Post-Treatment			ıt
	Main Study					To be repeated beyond 8 cycles				~ 0	- 11	Survival	
Treatment Cycle/Title:	Screening (Visit 2)	1	2	3	4	5	6	7	8	Discon	Safety Follow-up	Follow Up Visits ^b	Follow- Up
Scheduling Window (Days):	-28 to -1		± 3	± 3	± 3	± 3	± 3	± 3	± 3	At time of Discon	30 days post discon		Every 12 weeks
Informed Consent	X												
Inclusion/Exclusion Criteria	X												
Demographics and Medical History	X		X	X	X	X	X	X	X	X	X	X	
Prior and Concomitant Medication Review	X	X	X	X	X	X	X	X	X	X	X	X	
Trial Treatment Administration ^c		X	X	X	X	X	X	X	X				
Post-study anticancer therapy status											X	X	
Survival Status	X	X	X	X	X	X	X	X	X	X	X	X	X
Review Adverse Events			X	X	X	X	X	X	X	X	X	X	
Full Physical Examination	X	X	X	X	X	X	X	X	X				
Directed Physical Examination										X	X	X	
Vital Signs and Weight	X	X	X	X	X	X	X	X	X	X	X	X	
ECOG Performance Status	X ^d	X	X	X	X	X	X	X	X	X	X	X	
Pregnancy Test – Urine or Serum β-HCGe	X												
PT/INR and aPTT	X												

Trial Period:	Treatment Cycles ^a								End of Treatment	Post-Treatment			
	Main Study					To b	e repeat	ted beyo	ond 8				Survival
Treatment Cycle/Title:	Screening (Visit 2)	1	2	3	4	5	6	7	8	Discon	Safety Follow-up	Follow Up Visits ^b	Follow- Up
Scheduling Window (Days):	-28 to -1		± 3	± 3	± 3	± 3	± 3	± 3	± 3	At time of Discon	30 days post discon		Every 12 weeks
CBC with Differential	X	X	X	X	X	X	X	X	X	X	X	X	
Comprehensive Serum Chemistry Panel	X	X	X	X	X	X	X	X	X	X	X	X	
Hepatitis screening f	X												
Urinalysis	X									X			
T3, FT4 and TSH	X		X			X			X	X	X		
ECG	X												
Uric Acid	X		X		X		X						
Tumor Imaging	Xg			Xg			Xg						
Archival or Newly Obtained Tissue Collection ⁱ	X	X											
Correlative Studies Blood Collection j	X	X	X	X						X			

- a. Treatment cycles are 3 weeks
- b. Only for patients with ongoing treatment related toxicities. Details of required follow up visit are given in section 6.5.1 and 6.7.
- c. Siltuximab and spartalizumab given day 1 of each cycle except cycle 1 in the expansion phase
- d. ECOG performance status should be done within 10 days or less from day 1 of cycle 1
- e. Pregnancy test once a month women of child bearing potential

Protocol Study No: Winship4463-18 66

Product: Siltuximab plus Spartalizumab

Protocol/Version No.: 5, Date December 15, 2022

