12.5.1.2 Laboratory Data

Descriptive statistics for worst grade of each laboratory parameter by the NCI CTCAE scale version 4.0 at baseline and follow-up will be presented along with change from Baseline. Additionally, laboratory values ≥ Grade 3 severity will be tabulated and listed on an individual subject basis.

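### Uric acid is left off most on-treatment chemistry draws: one post-dose value falls in the 6-week DLT window, none after the second siltuximab dose, and none at cycles 3, 5 and 7

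*Combined protocol and SAP*

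**What the plan says.** **Testing schedule.** The screening chemistry in 8.1.2 includes the analyte ("ALP, ALT, AST, uric acid and albumin"). The on-treatment chemistry lists in 8.1.3, for Day 1 of each cycle and for "Days 8 and 15 (± 1 day) in cycle 1 and 2 ONLY", end with "total bilirubin, LDH, total protein, ALP, ALT, AST, and albumin" and do not name it; the end-of-treatment list omits it too. A separate Day 1 line in 8.1.3 adds "Uric acid every other cycle". The flow chart in 7.1 gives it its own row ("Uric Acid X X X X"), whose marks fall at screening and cycles 2, 4 and 6. Cycle 8, discontinuation and safety follow-up are blank.

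**Rules that use the value.** For siltuximab, section 6.3.3 sets the action by grade. Grade 1 or 2 continues with monitoring, and no interval is given. For the next grade it says "Grade 3 start therapy for hyperuricemia (allopurinol) and hold siltuximab until it resolves to grade 1", with resumption at a lower level. Grade 4 is a permanent hold. Table 7 in 6.2.3 counts other treatment-related non-hematologic toxicity of Grade 3 or higher in the first 6 weeks as a DLT, and also any AE that leads to permanent discontinuation of either drug. Section 9.1.2.1 treats a laboratory abnormality that triggers a protocol dose hold as an adverse event. Section 12.5.1.2 plans "Descriptive statistics for worst grade of each laboratory parameter".

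**The concern.** The plan itself identifies this toxicity. Section 4.1.2.1 lists hyperuricemia among the most common siltuximab reactions in the Castleman's disease study, which used 11 mg/kg, the same as dose level 2 here. The plan then attaches dosing consequences and possible DLT status to its grade, but measures it less often than the rest of the serum chemistry.

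A case that shows only as a laboratory value is not graded if it is not measured. It then triggers no hold, adds no DLT and does not appear in the worst-grade table. One measurement instead of five can lower the observed worst grade but cannot raise it. The question is how much of the decision period is uncovered, and how much that could matter.

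**Working it through.** **Inputs.** "Treatment cycles are 3 weeks" (7.1). The DLT window is 6 weeks, Days 1-42 (6.2.3). A patient without a DLT is evaluable only after at least two infusions of both drugs and 6 weeks of safety assessment (6.2.2). Chemistry days come from 8.1.3. The expansion stopping rule covers the first 8 weeks of treatment, Days 1-56 (12.1).

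**Placing the flow-chart marks.** The text extraction leaves room for doubt about columns, so I checked another row. Read the same way, the thyroid row lands on cycles 2, 5 and 8, which fits its schedule in 8.1.3 (cycle 2, then every third cycle). The uric acid marks then fall at screening and cycles 2, 4 and 6.

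**Calendar.** Nominal day = (cycle - 1) x 21 + day within cycle.

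| Visit | Day | Chemistry | Uric acid |
|---|---|---|---|
| C1D1 (pre-dose) | 1 | yes | no (screening value) |
| C1D8 | 8 | yes | no |
| C1D15 | 15 | yes | no |
| C2D1 (before infusion 2) | 22 | yes | **yes** |
| C2D8 | 29 | yes | no |
| C2D15 | 36 | yes | no |
| C3D1 | 43 | yes | no |
| C4D1 | 64 | yes | **yes** |

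- DLT window, after the first dose: chemistry on Days 8, 15, 22, 29 and 36; uric acid on Day 22 only, so 1 of 5.
- After the second infusion: the next uric acid value is on Day 64. The gap is 64 - 22 = 42 days, and the cycle 2 and cycle 3 doses are given within it. A patient can become evaluable for escalation with no value after dose 2.
- Cycles 1-8: 6 chemistry draws in cycles 1-2 plus 6 in cycles 3-8 = 12. Uric acid is on 3 of 12 (Days 22, 64, 106), or 4 of 12 if the text is taken to add cycle 8 (Day 148).

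**Expansion.** Sections 8.1.3 and 12.1 allow cycle 1 to be spartalizumab alone. First siltuximab is then on Day 22, after that day's blood draw. The next uric acid value, Day 64, lies beyond Day 56, so 0 values follow siltuximab in the 8-week window. Chemistry is nevertheless drawn on Days 29, 36 and 43.

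**Size.** Table 3 in 4.1.2.1 gives 6/53 = 11.3% any grade and 1/53 = 1.9% Grade 3-4, against 0 of 26 on placebo; this reproduces the stated 11% and 2%. As an illustration, assume the Grade 3-4 rate carries over, although it comes from another disease and 8 infusions rather than 2:

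- P(at least 1 in 6) = 1 - (52/53)^6 = 10.8%
- P(at least 2 in 6) = 1 - (52/53)^6 - 6 x (1/53) x (52/53)^5 = 0.5%
- P(at least 1 in 24) = 1 - (52/53)^24 = 36.7%

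The exact 95% interval for 1/53 is 0.05% to 10.1%. At its upper end, P(at least 2 in 6) would be 11.6%; at its lower end it is essentially zero.

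**The case against.** Several points on the other side are sound.

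- **Unscheduled tests are allowed.** Section 8.1 permits procedures at other times when clinically necessary. Section 6.3.3 calls for monitoring once Grade 1 or 2 is seen, so a raised cycle 2 value need not wait for cycle 4. Creatinine, potassium, phosphorus and calcium are on every chemistry panel, with a toxicity assessment at those visits. Before escalation, Grade 2 or higher events are reviewed and the DSMC must approve. All this stands, but it helps only once a case is suspected or already found.
- **Unequal frequency is general in this plan.** Hematology is not listed on Days 8 and 15, and thyroid tests are every third cycle. Section 12.2 makes all summaries descriptive. This stands, and limits what can be said about the tables. It does not explain why an analyte with its own hold and stop rules is left off blood already being drawn.
- **Any-grade hyperuricemia is not the relevant rate.** The 11% is mostly Grade 1-2, which is neither a DLT under the Grade 3 criterion nor a hold trigger. This stands.

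A reader might also infer more than the documents support.

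- *A 12-week gap, with four siltuximab doses between tests, after cycle 8.* This needs the flow-chart block for cycles 5-8 to repeat literally. The same reading would put imaging at cycles 10 and 14, although 8.1.3 and 14.3 say every 3 cycles, and it would break the thyroid schedule too. The text sets the recurring interval. For the same reason, the documents do not show coverage falling further with time on drug.
- *Doses given without a value on every odd cycle.* Cycle 1 has the screening value, and no siltuximab has been given by then. The gap is at cycles 3, 5 and 7.
- *A contradiction with 6.3.3.* No section makes a current uric acid value a condition of dosing. This is a weak design choice; the rules do not conflict.
- *A bias towards escalation.* Under-detection can only lower the count, but at the 1/53 rate hyperuricemia alone would almost never change a cohort decision.

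**Conclusion.** The point holds as a gap in safety ascertainment with a modest expected effect. The firm part is the schedule: 1 of 5 post-dose chemistry draws in the DLT window carries uric acid, none follows the second infusion until Day 64, and cycles 3, 5 and 7 have no scheduled value for the grade-based rules. Spartalizumab-first expansion patients have none after siltuximab in the 8-week stopping window.

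This rests on the flow chart's even cycles and on counting 8 weeks from the first study treatment. If the wording in 8.1.3 were instead taken to mean odd cycles, the only value in the DLT window would be on Day 1, before any drug. Spartalizumab-first patients would then have a Day 43 value.

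The effect on escalation rests on a single Grade 3-4 case in 53 patients with another disease and longer exposure: about 0.5% for two or more cases in six, with wide uncertainty. That figure is also the chance that such cases occur, not that they are missed; the Day 22 test and clinical detection would find some. The documents do not reproduce the CTCAE thresholds for hyperuricemia, so the share of Grade 3-4 cases that would be silent cannot be estimated from them.

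**What to change.** In 8.1.3, add uric acid to the serum chemistry lists for Day 1 of every cycle and for Days 8 and 15 of cycles 1 and 2, and delete the separate alternate-cycle line. In 7.1, make the uric acid row match, including the blank cycle 8 cell, so that text and chart give one schedule.

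Scheduled post-dose coverage in the DLT window rises from 1 of 5 to 5 of 5, and over cycles 1-8 from 3 of 12 to 12 of 12 draws. For spartalizumab-first expansion patients, values after siltuximab within 8 weeks rise from 0 to 3 (Days 29, 36 and 43).

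The cost is one more analyte on blood already drawn: a small laboratory fee and a schedule edit. No visit, sample, dose, hold rule or stop rule changes.
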